# 10.3.3 Secondary outcome analysis

Secondary outcomes are exploratory and none are powered for statistical significance. Secondary outcomes that are measured as continuous variables (difference in daily urine output; difference in weight from baseline to day 4; difference in change in serum sodium potassium, bicarbonate, urea, creatinine, and estimated glomerular filtration rate between baseline and day 4; urinary electrolyte concentrations at day 2 and day 4; inferior vena cava diameter; change in breathlessness score (Likert scale); time to clinical euvolaemia; and length of stay) will be assessed using independent samples t-test, and unadjusted linear regression (with treatment assignment as the independent variable), and linear regression adjusted for daily salt intake and median number of hours of furosemide per day.

Secondary outcomes that are measured as categorical variables (incidence of hyponatraemia, hypochloraemia, hypokalaemia, metabolic alkalosis (serum bicarbonate concentrations >29 mmol/L) or metabolic alkalosis (serum bicarbonate concentrations <23 mmol/L); clinical assessment of congestion; proportion of patients with IVC diameter >2cm; proportion of patients with JVD ratio <4; rate of adverse and serious adverse events; rate of drop-out after randomisation will be assessed using chi-squared tests, un-adjusted logistic regression (with treatment assignment as the independent variable), and logistic regression adjusted for daily salt intake and median number of hours of furosemide per day.

Survival analysis (time to cause specific hospitalisation and time to cause specific mortality) will be conducted with a time-to-first event analysis using Kaplan-Meier and logrank tests, un-adjusted Cox proportional-hazard outcome models.

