# 3.5 Secondary endpoints/outcomes

All secondary endpoints are exploratory designed to inform future research.

Differences between the two groups during the 4 day treatment period in:

1) daily weight

2) serum electrolyte levels (sodium, bicarbonate and potassium)

3) incidence of electrolyte abnormalities; hyponatraemia (<135 mmol/L), hypochloraemia (<96 mmol/L), hypokalaemia (<3.5 mmol/L), high (>30 mmol/L) or low (<22 mmol/L) serum bicarbonate.

4) change in renal function measured by serum creatinine (µmol/L) and estimated glomerular filtration rate (eGFR) (ml/min/1.72m2)

5) change in urinary electrolyte levels after 48 and 96 hours of treatment; sodium, chloride, potassium.

- 6) clinical assessment of congestion
- 7) ultrasound measures of congestion period; inferior vena cava (IVC) diameter
- 8) change in breathlessness score using the Likert scale.
- 9) time to clinical euvolaemia and end of intravenous therapy

10) length of stay

11) rate of adverse reactions, serious adverse reactions and suspected unexpected serious adverse reactions – treatment arm

- 12) rate of adverse events and serious adverse events both arms
- 13) rate of recruitment to study
- 14) time taken to screen & recruit
- 15) rate of drop-out after randomisation cause specific
- 16) Cause specific hospitalisation or mortality after 30 days and 180 days follow up.

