#### 7.9 Withdrawal criteria

Patients can be withdrawn from the trial if:

- They withdraw their consent at any point during the study **for any reason**. This can happen at any time after consent and during follow up. In such an event no additional data will be collected from the patient and there will be no follow up. The study doctor will ascertain whether the patient wishes the withdrawal of consent to apply retrospectively to the withdrawal (i.e. can we use data already collected?). The outcome of any and all discussions regarding the withdrawal of consent will be documented in the medical notes and case report form.
- A patient's condition deteriorates due to heart failure or another pathology to the extent that they are expected to die within the next 24 to 48 hours.
- The study doctors deems the risk of continuation due to serious drug reactions or adverse events is too great to the patient. This will be fully discussed with the patient and the content and outcome of all discussions will be documented in the medical notes and CRF.
  - Worsening symptoms of heart failure\*
  - Hyponatraemia (<135 mmol/L)
    - Asymptomatic\*
      - Severe (<130 mmol/L)\*

    - Symptomatic (confusion, drowsiness, nausea or vomiting)\*\*
  - Hypotension
    - Asymptomatic\*
    - Symptomatic with no sequelae\*
    - Symptomatic with significant sequelae i.e. fall due to postural hypotension\*\*
  - o Hyperchloraemia
    - Mild 107 110 mmol/L\*
    - Severe >110mmol/L\*\*
  - Worsening renal function
    - >30% increase in serum creatinine from admission. \*
    - >50% increase in serum creatinine from admission.\*
    - >100% increase in serum creatinine from admission.\*\*
  - Side effects of acetazolamide: haemorrhage, ataxia, depression, diarrhoea, dizziness, fatigue, flushing, irritability, headache, loss of appetite, nausea, vomiting, taste disturbance, paraesthesia,
    - Tolerable to the patient.\*
    - Intolerable to the patient.\*\*

\* - Clinically relevant safety endpoint that would not automatically lead to the discontinuation of the study drug. Withdrawal would be at patient's request or the study doctor's discretion if the risk of continuation was deemed too high.

\*\* - Occurrence would lead to withdrawal from the study if it occurred in the acetazolamide arm

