We will attempt to replace patients that withdraw from the trial prior to completing day 4 assessments. The reason(s) for withdrawal will be carefully monitored for trends in patient opinions of participation in the study, adverse drug reactions or adverse events.

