# 10.6 Subject population

As this is a pilot and exploratory study, we will perform both an intention to treat analysis on all patients completing the study so that we can most accurate describe the clinical effects of ACZ including tolerability and side effects and a per-protocol analysis so we can most accurately assess the primary endpoints.

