# 10.7 Procedure(s) to account for missing or spurious data

We will attempt to replace any patient with data missing for either primary endpoint (i.e. those who did not complete 4 days of treatment, those with data on net fluid loss missing on any day, and those with data on serum chloride missing on baseline or day 4). However, we expect missing data to be a minor problem as data collection for net fluid loss will be done by the study team during each visit and data on chloride concentrations will be collected as part of routine care. Reasons for missing data will be recorded in a dedicated section within the CRF for each study visit. We will not perform any imputation of missing data.

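### Renal change is compared at day 4 in completers, but early creatinine doubling forces withdrawal in the acetazolamide arm only, so the between-arm comparison can be biased

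*Protocol*

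**What the plan says.** All references are to the protocol.

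- **Endpoint.** Section 3.5 lists change in creatinine and eGFR among the "Differences between the two groups during the 4 day treatment period in" set of secondary outcomes.
- **Analysis.** Section 10.3.3 makes this "difference in change in serum sodium potassium, bicarbonate, urea, creatinine, and estimated glomerular filtration rate between baseline and day 4", tested by t-test and linear regression on one change per patient. In the schedule (7.7) the day-4 blood sample is the 72 h sample.
- **Population.** Section 10.6 describes an "intention to treat analysis on all patients completing the study". The per-protocol set in 10.1 is also limited to patients who completed.
- **Withdrawal rule.** In 7.9 a ">100% increase in serum creatinine from admission" carries the double asterisk, which means: "Occurrence would lead to withdrawal from the study if it occurred in the acetazolamide arm". No compulsory rule covers controls; their withdrawal is left to the patient or the study doctor.
- **Replacement and missing data.** Section 7.9: "We will attempt to replace patients that withdraw from the trial prior to completing day 4 assessments". Section 10.7 extends replacement to "those who did not complete 4 days of treatment" and rules out imputation.
- **Other capture.** Section 9.2 records all adverse events, 9.3 adds any clinically significant abnormal laboratory value, and 3.5 includes drop-out by cause.

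**The concern.** A patient's absence from the day-4 comparison can depend both on the arm and on the outcome being compared. If creatinine doubles at 24 or 48 h on acetazolamide, the patient must be withdrawn and is replaced if possible. The same event in a control does not force withdrawal. A t-test does not correct for this, nor does a regression adjusted for salt intake and furosemide hours.

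This matters because section 4 gives feasibility and tolerability as the primary aim, 2.2 names renal dysfunction as a risk of the combination, and Appendix 1 expects worsening renal function in controls too. Separating a drug effect from that background needs the early declines of both arms, and section 2 intends the results to inform a larger trial.

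No second renal display fills the gap. Section 10.3.3 plans incidence analyses for sodium, chloride, potassium and bicarbonate abnormalities but none for renal decline. Yet the footnote in 7.9 treats creatinine rises above 30% and above 50% as clinically relevant safety endpoints.

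**Working it through.** The plan states no figure for this point, so there is none to reproduce. The rules are followed through first; the arithmetic then shows what they can do.

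**Who leaves the comparison**

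1. A doubling first seen at 72 h still supplies a day-4 value. Only doublings at 24 or 48 h are affected.
2. On acetazolamide, such a patient is withdrawn (7.9), has not completed four days of treatment (10.7), falls outside a completer population (10.6) and has no value imputed (10.7).
3. In the control arm, the same patient may continue and be counted.

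**Illustration**

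Assumed inputs, none from the documents: 20 analysed per arm; Day 1 creatinine 120 µmol/L and equal to admission; one patient per arm with a +110% rise (+132 µmol/L) at 48 h that would last to day 4; all others averaging +10 µmol/L.

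| Case | Acetazolamide mean change | Control mean change | Difference |
|---|---|---|---|
| Everyone kept | (19×10 + 132)/20 = 16.1 | 16.1 | 0 |
| Acetazolamide patient replaced by a +10 patient, control stays | 10.0 | 16.1 | -6.1 |
| Both replaced | 10.0 | 10.0 | 0 |
| Separate case, +60% rise (+72) in one patient per arm: control de-escalated and replaced, acetazolamide patient continues | (19×10 + 72)/20 = 13.1 | 10.0 | +3.1 |

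Range of the second case:

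- 25 per arm, Day 1 creatinine 100: 10 - (24×10 + 110)/25 = -4.0
- 16 per arm, Day 1 creatinine 150: 10 - (15×10 + 165)/16 = -9.7

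**Does the adverse-event definition replace the comparison?**

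The named renal adverse event in 9.2 is an eGFR fall above 50%. The formula for the eGFR endpoint is not stated, so eGFR is taken as proportional to creatinine to the power -k, with k from 1.0 to 1.2. If creatinine is multiplied by m, the fall is 1 - m^(-k).

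- +30% (m = 1.3): fall of 23.1% to 27.0%
- +50% (m = 1.5): fall of 33.3% to 38.5%
- A 50% fall needs m = 2.00 (k = 1.0) or 1.78 (k = 1.2)

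The smaller rises named in 7.9 therefore do not meet that definition by themselves. The serious-event limit of creatinine above 221 µmol/L catches a +50% rise from above 221/1.5 = 147 and a +30% rise from above 221/1.3 = 170. Section 9.3 can bring in the rest if judged clinically significant. That is case-by-case recording, not a count at fixed thresholds in both arms.

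**The case against.** The strongest reply is that little is lost. The illustrated patient reaches 120×2.1 = 252 µmol/L, above the 221 limit in 9.2, and is a serious adverse event reportable within 24 hours. The withdrawal also appears in drop-out by cause, and 7.9 promises to monitor withdrawal reasons. This stands: a reader might infer that the doubling disappears from safety reporting, and it does not. But the drop-out endpoint shows the withdrawn acetazolamide patient and not the control who stays, so it is no like-for-like comparison.

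Four further stronger readings fail:

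- **That data collection stops after a safety withdrawal.** The sentence "In such an event no additional data will be collected from the patient" concerns withdrawn consent only. Loss of a safety withdrawal is inferred from 10.6 and 10.7. The inference could be softened, since 7.8 retains the data of patients de-escalated early and even calls them completed; but nothing says that a safety withdrawal's creatinine enters the comparison.
- **That the bias favours acetazolamide.** De-escalation of furosemide (7.8) ends study investigations in either arm, although routine-care bloods may still give a day-4 value. Net direction is unknown.
- **That rises of 30% to 50% escape recording.** Section 9.3 can capture them.
- **That 3.5 and 10.3.3 contradict each other.** A change from baseline to day 4 lies within the treatment period; the difficulty is who contributes to it.

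It is also fair that the endpoint is exploratory and unpowered, and that the trigger runs from admission while the endpoint runs from Day 1, so a patient withdrawn for doubling need not have doubled from Day 1.

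**Conclusion.** The point holds as a limited one. As written, the day-4 renal comparison can lose early creatinine doublings by a rule that binds one arm only, so it can be biased, and no planned analysis shows renal decline by arm in all randomised patients.

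Neither the size nor the net direction can be derived from the documents. The -6.1 µmol/L (range -4.0 to -9.7), 0 and +3.1 results rest entirely on assumed inputs, and early doubling may be rare. The conclusion depends on reading completion in 10.6 as excluding patients withdrawn for safety before day 4, which is the natural reading alongside 7.9 and 10.7. It does not depend on any claim that safety events go unrecorded. The change is worth making because it is cheap and serves the trial's stated tolerability aim.

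**What to change.** In 10.3.3:

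1. Analyse renal function in all randomised patients with a post-baseline creatinine, unless consent to use their data is withdrawn. Include the sample that triggered withdrawal and any routine-care values up to day 4. Use peak creatinine and lowest eGFR.
2. Add descriptive by-arm counts of creatinine rises above 30%, 50% and 100%. State Day 1 as the reference, and show admission as well because the withdrawal trigger uses it.
3. Keep the day-4 change in completers as supportive.

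Cost: a few table rows. Creatinine is already scheduled on days 1 to 4 (7.7) from routine-care blood (7.10), so no tests are added. Intervals will be wide. With an assumed 20 per arm, 6 versus 3 events gives 6/20 - 3/20 = 15 percentage points, with a Newcombe 95% interval of -11 to 39. The rows should therefore be presented as description, not as a test.

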Whether acetazolamide has a significant diuretic effect in patients also taking standard treatment in the UK (240mg / 24 hours IV furosemide infusion) is unknown. Furthermore, how it affects renal chloride excretion and whether it can correct hypochloraemia or prevent incident hypochloraemia due to high dose loop diuretic is unknown.

There is a pressing need to clarify whether or not acetazolamide can increase diuresis and / or favourably affect renal chloride excretion. Our pilot and exploratory study will provide data to estimate the effect of acetazolamide on diuresis and serum chloride concentrations during treatment with IVI of furosemide at 10mg/hr (standard of care in the UK for patients admitted with severe venous congestion).

It will also provide data on the possible tolerability of acetazolamide and recruitment rate to a study of acetazolamide in patients hospitalised with heart failure in the UK.

Should the data suggest a favourable effect on either diuresis and / or chloride homeostasis during diuresis then the results of study will be used to design a large multi-centre randomised placebo controlled trial of acetazolamide combined with high dose loop diuretics to prevent or correct hypochloraemia during in-patient diuresis.

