# 7.6 Baseline data

- Medical history including age (years), sex, co-morbidities, and aetiology of heart failure
- Bedside observations including body weight, systolic and diastolic blood pressure, heart rate and rhythm.
- Patient symptoms including: investigator assessed New York Heart Association class, peripheral oedema severity (none = 0, trace = 1, ankles = 2, below knees = 3, above knees = 4, sacral = 5), pulmonary congestion severity (lung crackles) (absent = 0, bibasal = 1, midzone = 2, whole lung = 3), jugular venous pressure severity (not visible = 0, 1-4cm above the sternal notch = 1, >4cm above the sternal notch = 2, up to the earlobes = 3), patient assessed symptoms using the Likert breathlessness scale (patients will be asked to rate their breathlessness severity on a 5-point scale of: 1=not short of breath, 2=mildly short of breath, 3=moderately short of breath, 4=severely short of breath, 5=very severely short of breath)

- Echocardiographic data including: left ventricular ejection fraction either calculated by SimpsonSHS Trust biplane method or qualitatively on transthoracic echocardiogram performed either as routine practice or by the investigator, presence of moderate or worse valve disease, inferior vena cava diameter
- Biochemical data including: NTproBNP, haemoglobin (g/dL), haematocrit (fraction), sodium (mmol/L), chloride (mmol/L), potassium (mmol/L), bicarbonate (mmol/L), creatinine (µmol/L), urea (mmol/L).
- Data on pre-admission medical and device therapy including: angiotensin converting enzyme inhibitor, angiotensin receptor blocker, sacubitril valsartan, beta-blocker, mineralocorticoid receptor antagonist, oral loop diuretic dose, presence of cardiac resynchronisation therapy device, presence of implantable cardioverter defibrillator, cumulative dose of in-patient loop diuretic (mg / day)

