# Hull University Teaching Hospitals

Г						T		NHS
NTproBNP	X (RC)		X ( if not performed on admission)					
Eligibility assessment		Х						
Randomisation		Х						
Intravenous Furosemide infusion at 10mg/hr (standard of care)***	х		x	X****	X****	х		
Dispensing of trial drugs (Acetazolamide arm only)		x						
Acetazolamide given to the patient			x	Х	Х	Х		
Compliance with medication and diet sheet				X (previous day)	X (previous day)	X (previous day)	X (previous day)	
Oral intake – mL				X (previous day)	X (previous day)	X (previous day)	X (previous day)	
Urine output		Х	Х	X (previous day)	X (previous day)	X (previous day)	X (previous day)	
Urine electrolytes					X (previous day)		X (previous day)	
Likert breathlessness scale			Х	Х	X	Х	X	
Diet Sheet		X (x4 given to the patient)	Х	X (previous day)	X (previous day)	X (previous day)	X (previous day)	
Catheter sited (to measure urine output / jug used)		x						
Clinical assessment of congestion			X	X	X	X	X	
Ultrasound assessment of congestion			X				X	
Adverse event / reaction assessments				Х	Х	Х	Х	

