#  Visit 3 - Day 2 – 24 hours

- Furosemide infusion to continue if clinically indicated
  - If patient deemed to not require standard of care by day 2 and has their diuretic treatment de-escalated efforts will be made to replace patient. All data collected will be retained but patient will have "completed" the study early.
- Vital signs measured by nursing staff
- Bloods taken
  - Urea and electrolytes
  - o Full blood count
- Acetazolamide 250mg to be given by ward staff in the morning (24 hours after first dose) and 6 hours later (in ACZ group only) as per electronic prescription
- Ongoing input from treating team: ward round and any input that stems from that, regular observations from nursing staff, input from other health professionals if indicated (for example dieticians, physiotherapists, occupational therapists)
- Study doctor visit (24 hours +/- 2 hours from first dose of ACZ (ACZ arm) or randomisation (SoC arm)
  - Clinical examination and medical history
  - o Diet sheet collected from previous day
  - Fluid balance and urine output
  - o 24 hour urine collection to begin 24 hours from first dose of ACZ or randomisation
    - Patient asked to empty bladder or nursing staff to empty catheter bag and then begin urine collection
  - o Patient assessed breathlessness using 5-point Likert breathlessness scale

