# Visit 5 - Day 4 – 72 hours

- Furosemide infusion to continue if clinically indicated
  - If patient deemed to not require standard of care by day 4 and has their diuretic treatment de-escalated the patient will be deemed to have completed the study and further study-related investigations not carried out.
  - Body weight, blood pressure and heart rate measured by nursing staff
- Bloods taken

.

- o Urea and electrolytes
- o Full blood count
- Acetazolamide 250mg to be given by ward staff in the morning (72 hours after first dose) and 6 hours later (in ACZ group only) as per electronic prescription
- Ongoing input from treating team: ward round and any input that stems from that, regular observations from nursing staff, input from other health professionals if indicated (for example dieticians, physiotherapists, occupational therapists)
- Study doctor visit (72 hours +/- 2 hours from first dose of ACZ (ACZ arm) or randomisation (SoC arm)
  - o Clinical examination and medical history
  - Diet sheet collected from previous day
  - o Fluid balance and urine output
  - o 24 hour urine collection to begin 72 hours from first dose of ACZ or randomisation
    - Patient asked to empty bladder or nursing staff to empty catheter bag and then begin urine collection
  - Patient assessed breathlessness using 5-point Likert breathlessness scale

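### Urinary electrolytes are analysed only as concentrations, which cannot separate dilution from reduced chloride excretion, and the stated change has no baseline

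*Protocol*

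**What the plan says.** The Trial Summary and section 3.5 of the protocol list as a secondary endpoint the "change in urinary electrolyte levels after 48 and 96 hours of treatment; sodium, chloride, potassium". Section 10.3.3 names the variable to be analysed as "urinary electrolyte concentrations at day 2 and day 4". It is compared between arms by t-test and by linear regression, first unadjusted and then adjusted for salt intake and hours of furosemide.

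The question these data serve is in section 2. Among the unknowns given there is "how it affects renal chloride excretion and whether it can correct hypochloraemia".

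The collections are fixed in sections 7.7 and 7.8. The schedule row "Urine electrolytes" is marked only at the 48-hour and 96-hour visits, each for the previous day. The Day 2 visit says "24 hour urine collection to begin 24 hours from first dose of ACZ or randomisation" and the Day 4 visit says "24 hour urine collection to begin 72 hours from first dose of ACZ or randomisation". The baseline biochemistry in section 7.6 lists serum analytes and no urinary electrolyte, and the baseline table in section 10.3.1 has none either.

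**The concern.** Two separate matters arise.

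The first is the scale. Excretion is concentration multiplied by volume. The primary hypothesis in section 3.2 is that acetazolamide increases diuresis, so treatment is expected to move the volume by which the excreted amount is divided. Randomisation does not remove this, because urine volume is itself a treatment effect, and the planned adjustment covariates do not include it. A lower urinary chloride concentration in the acetazolamide arm could mean that the kidney excretes less chloride, or that the same chloride is passed in more water. Section 10.3.3 fixes the scale that cannot distinguish the two.

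The second is the wording. The endpoint is called a change, but there is no pre-treatment urine electrolyte from which to measure one.

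What is at stake is the reading of the trial's only direct data on renal chloride handling. The trial is meant to inform a larger one, and these collections are done outside routine care.

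**Working it through.** No figure in the protocol exists to reproduce for this endpoint, so the check measures how far volume alone moves the concentration.

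**Inputs**
- Expected net fluid loss in control: 1000 mL/day (section 10.1).
- Difference sought between arms: 500-1000 mL/day (section 10.1).
- Net fluid loss is built from intake and urine volume (section 3.4), so urine volume = intake + net loss.
- Intake is not given in the protocol. Assumed: 1000, 1500 or 2000 mL/day, the same in both arms.

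**Formulas**, with V0 the control and V1 the acetazolamide urine volume:
- V0 = 1000 + intake, and V1 = V0 + 500 or V0 + 1000.
- Shift in concentration at equal excretion = V0/V1 - 1.
- Rise in excretion hidden at equal concentration = V1/V0 - 1.

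| Intake (mL) | V0 (mL) | V1 (mL) | Concentration at equal excretion | Excretion rise hidden at equal concentration |
|---|---|---|---|---|
| 1000 | 2000 | 2500 | -20.0% | +25.0% |
| 1000 | 2000 | 3000 | -33.3% | +50.0% |
| 1500 | 2500 | 3000 | -16.7% | +20.0% |
| 1500 | 2500 | 3500 | -28.6% | +40.0% |
| 2000 | 3000 | 3500 | -14.3% | +16.7% |
| 2000 | 3000 | 4000 | -25.0% | +33.3% |

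The percentages depend only on the ratio of the volumes, so no chloride concentration has to be assumed. A true 10% rise in excretion gives 1.1 x V0/V1 - 1, which runs from -5.7% (3000 to 3500 mL) to -26.7% (2000 to 3000 mL). The concentration would fall although excretion had risen. On the amount scale, equal excretion gives a difference of zero in every row.

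**The stated change.** The first collection runs from 24 to 48 h and the second from 72 to 96 h after the first dose or randomisation. Both are on treatment. The only change that can be computed is from the first collection to the second, and section 10.3.3 does not analyse that; it uses the values at the two time points. The endpoint definition and its analysis therefore differ.

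**The case against.** The strongest reply is that a lower concentration at equal excretion is not simply a false signal. The co-primary is a serum concentration. If two patients excrete the same chloride and one passes more water, that patient loses less chloride per litre, which tends to hold serum chloride up. That is one reasonable meaning of chloride sparing. Total excretion has the opposite weakness, since a stronger diuresis can raise it even when each litre carries less chloride. This stands, and is the reason to keep concentrations in the report beside excretion.

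Second, section 10.3.3 also compares daily urine output between arms, and net fluid loss is a co-primary, so a fall in concentration with a rise in volume would be partly visible. This also stands. It does not supply a comparison of excretion, which needs each patient's concentration multiplied by that patient's volume.

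Third, deriving an amount from a timed collection could be left to a statistical analysis plan. The word used in section 3.5 would allow that, but section 10.3.3 itself names concentrations.

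A reader might also infer that the t-test would report chloride sparing. The protocol does not support this: it gives no standard deviation for urinary chloride, and section 10.3.3 says that no secondary outcome is powered. Nor does the missing baseline invalidate the comparison, because randomised arms can be compared at each time point without one.

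**Conclusion.** The point holds in a limited form. Concentration alone does not answer the question about excretion in section 2. Volume alone would lower it by about 14-33% at equal excretion, and equal concentrations would hide a rise of 17-50%. These ranges rest on an assumed intake of 1-2 L/day, equal in both arms, and on the 500-1000 mL/day difference appearing entirely as urine. The size depends on the assumed intake; the direction does not, as long as acetazolamide raises urine volume.

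The change named in the summary and section 3.5 cannot be a change from baseline. That is a fault of definition, separate from dilution.

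The consequence is confined to an exploratory secondary endpoint. A reader might extend it to the chloride co-primary, but that is serum chloride, measured and tested on its own, and nothing here alters it, the sample size or a safety rule.

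**What to change.** In section 10.3.3, make the analysed variable the 24-hour excretion of sodium, chloride and potassium (concentration x collected 24-hour volume, in mmol/24 h) for 24-48 h and for 72-96 h, compared between arms at each collection. Report concentrations alongside it. In the Trial Summary and section 3.5, replace the wording about a change with this definition.

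The cost is wording in three places. Timed 24-hour collections are already planned, and urine output for the same days is already recorded at the 48-hour and 96-hour visits. The drawback is minor: excretion depends on a complete collection, so incomplete ones should be marked as such in the case report form.
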